### 2.3. Primary outcome measures

Participants gave blood and stool samples a day before intervention with barley beta-glucans. Blood sampling was performed for insulin resistance determination and for lipid profile determination (Total cholesterol, HDL-cholesterol, LDL-cholesterol, triglycerides). They also had option to give a blood sample for genetic investigation of genes associated with lipid metabolism (apoE).

Analysis were performed in accordance with health community centres in Ajdovščina and Ljubljana, Slovenia. Venous blood samples were obtained by professional medicine personnel for analysis of fasting glucose, lipids and insulin.

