### 1.2. Hypothesis

1. 4- week consumption of beta-glucans alters the composition of intestinal microbiota and changes the ratio of different bacteria groups and consequently effects production of short chain fatty acids in a population with metabolic syndrome or with high risk for metabolic syndrome development.
2. 4- week consumption of beta-glucans has an influence on glucose metabolism and consequently improves insulin resistance within people with metabolic syndrome or with high risk for metabolic syndrome development.
3. 4 - week consumption of beta-glucans improves specific plasma lipid content in a population with metabolic syndrome or with high risk for metabolic syndrome development.

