#### 2.3.2. Oral glucose tolerance test (OGTT)

OGTT was performed one day before and one day after the four-week intervention [7]. Participants fasted overnight (for at least 10 hrs). Fasting blood samples were obtained for analysis of baseline glucose and insulin levels. After the consumption of glucose solution (75 g of glucose dissolved in 250 ml of water) in five minutes time, blood samples were taken, at 30, 60 and 120 minutes. Concentrations of blood glucose were determined with a standardised spectrophotometric methodology (Roche Hitachi Cobas c system (GLUC3)). The procedure is based on hexokinase and glucose-6-phosphate dehydrogenase reaction [8]. Blood insulin was determined by immunoradiometric assay (Biosource Europe S.A., Nivelles).

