#### 2.3.3. Faecal sampling and DNA isolation

Faecal samples were collected one day before the start and at the end of the intervention. The samples were frozen immediately and stored at -20 °C until use. DNA was isolated within one week after sampling. DNA isolation was performed in parallel using the protocol for isolation of DNA from faecal samples described by Yu and Morrison (2004) [9].

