#### 2.3.4. Microbial community analysis

**DGGE:** PCR-DGGE fingerprinting was performed to check the quality of isolated DNA between parallel samples and to compare the individual profiles. PCR-DGGE analysis was performed as described by Matijašić et al. (2014) [10].

**Real-time PCR analysis** was performed by an established procedure for quantification of bacteria in faecal samples [10] with slight modifications using a ViiA™ 7 Real Time PCR System (Applied Biosystems, USA). Data were analysed with ViiA™ 7 Software 1.2.2 (Applied Biosystems, USA).

**Next generation pair end sequencing:** For 16S rRNA sequencing, 23 participants were chosen randomly among those with both samples qualified for sequencing after DGGE examination. In total, 46 samples from 14 persons in the test group and nine persons in the control group were examined.

The Illumina Miseq platform with v.3 2x300 pair end technology was used for sequencing V3 and V4 16S rRNA regions (Microsynth). After demultiplexing, raw reads were processed following the UPARSE pipeline (Usearch v.8, June 2015) [11]. Stringent quality filtering based on a low expected number of errors was used for OTU formation with algorithm parameters optimized after mock sample analysis (34 strains). With relaxed quality filtered sequences, more than 91 % of raw reads could be placed into an OTU with a 0.03 distance criterion. Presumptive OTU identity was determined with the 'usearch\_global' function searched against Silva NR SSU v.119 and LTP SSU type strains v.121 database. Taxonomy was assigned to OTUs with Wang et al.'s (2007) [12] method implemented in Mothur v.1.35 and the RDP training set 14 [13]. FastTree2 was used for the generation of an approximately maximum-likelihood phylogenetic tree [14]. Taxonomy, the OTU table and the phylogenetic tree were handled with the 'R' package Phyloseq for statistical analysis and graphics [15].

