## 2.4. Secondary outcome measures

After 4 weeks of dietary intervention protocol of primary outcome measures was repeated.

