## 2.5. Missing data

Due to complex presentation of data for changes in gut microbiota composition, we can't provide results for primary and secondary outcome measure of microbiota composition.

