## 3. STATISTICS

For analysis of participants' anthropometric and metabolic characteristics, RT-PCR results and microbial richness and diversity measures, a Wilcoxon signed-rank test or paired samples *t*-test were used as appropriate with  $P < 0.05$  for significance and  $P < 0.1$  for reporting a trend (SPSS v.21). Statistical sequence analysis was based on differential abundance testing using the 'R' package DESeq 2 [16]. Differential abundance that occurred in test group subjects after dietary intervention but not in the control group was determined in a model with interaction (time, group and subject). Significance was reported for  $P < 0.05$  after multiple inference correction (Benjamini-Hochberg), and all OTUs with  $P < 0.05$  before correction were screened for trends. Initial microbial abundance differences between test group subjects who responded to dietary intervention with a 10 % plasma total cholesterol concentration drop and those without reduction were also tested with Deseq2 [16]. OTUs with  $P < 0.1$  after correction were considered significant. Alpha and beta diversity measures and PCoA of weighted UniFrac distances were calculated and plotted with Phyloseq [15].

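### SAP 2.3 and 2.4 separate primary from secondary outcomes by time point, in conflict with the SAP's own sampling times, analyses and hypotheses

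*SAP*

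**What the plan says.** SAP section 2.3 carries the primary outcome heading and begins: "Participants gave blood and stool samples a day before intervention with barley beta-glucans". It then lists what the blood was used for: insulin resistance and four lipids (total, HDL and LDL cholesterol, triglycerides). Section 2.4 carries the secondary outcome heading and consists of one sentence: "After 4 weeks of dietary intervention protocol of primary outcome measures was repeated". It names no other variable. Section 2.5 uses the same labels when it says that "we can't provide results for primary and secondary outcome measure of microbiota composition".

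The subsections of 2.3 give other times. Section 2.3.2 states: "OGTT was performed one day before and one day after the four-week intervention". Section 2.3.3 states: "Faecal samples were collected one day before the start and at the end of the intervention". Section 2.3.1, on lipids, describes assays only and gives no sampling time.

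The three hypotheses in section 1.2 all concern the effect of four weeks of consumption; the lipid one reads, in part, "4 - week consumption of beta-glucans improves specific plasma lipid content". The protocol schedules measurements before and after the intervention and ranks no outcome as primary or secondary.

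**The concern.** A primary outcome should say which variable is measured, when, and what is compared with what. Here the only stated difference between primary and secondary is the visit. Read by the headings, the primary outcome is a value taken before any study bread was eaten, and the value that bears on the hypotheses is secondary. No outcome is defined as a change or as a comparison between the two breads.

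What is at stake is reporting. If results are tabulated under these labels, the primary table shows how alike the arms were at entry, and the informative measurements appear one rank lower. A reader cannot tell from the SAP which result the trial was meant to stand on.

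**Working it through.** The documents give no sample size, power or effect-size figure for this point, and none is needed. The check sets the sections side by side, with one count.

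1. **Headings.** Section 2.3 (primary) opens with the day-before sample. Section 2.4 (secondary) is the same protocol repeated at four weeks. The variables are the same and the times differ, so the split is by time point. Section 2.5 fits this, since it speaks of a primary and a secondary measure of one variable, microbiota composition.

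2. **OGTT.** Section 2.3.2, under the primary heading, places the test both before and after the intervention. This contradicts the split in step 1.

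3. **Stool samples.** Section 2.3.3, also under the primary heading, gives both times. Section 2.3.4 confirms it by count: "In total, 46 samples from 14 persons in the test group and nine persons in the control group were examined". Persons: 14 + 9 = 23. Two samples each: 23 × 2 = 46, which equals the stated total. Week-4 stool samples are therefore described inside the primary section.

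4. **Lipids.** Section 2.3.1 gives no time, so the opening of 2.3 is the only timing for lipids in that section, and it is baseline. Elsewhere it is clear that later values exist. The protocol's lipid form (part B, item 1) has before and after columns, and section 3 of the SAP defines responders by a 10 % fall in total cholesterol, which requires a later value. Neither place corrects the label.

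5. **Analyses.** For metabolic measures, RT-PCR and diversity, section 3 uses "a Wilcoxon signed-rank test or paired samples" *t*-test. A paired test needs both visits. For sequence data it uses a model with interaction in time, group and subject, which also needs both. Section 3 never uses the words primary or secondary, so it ties no analysis to a primary outcome. For the metabolic measures the paired tests are within person, and no test-versus-control contrast is stated.

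6. **Hypotheses.** All three in section 1.2 concern four-week effects. A baseline value alone cannot address them.

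Steps 2, 3, 5 and 6 each conflict with the split in step 1. Step 4 leaves it uncorrected within 2.3.

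**The case against.** The strongest reply is that this is loose wording with no consequence. The sentence that opens 2.3 describes a sampling procedure and does not formally define an endpoint. Section 1 says the document gives basic information and was prepared once the trial was complete. The subsections of 2.3 include post-intervention OGTT and stool samples, and every paired or interaction analysis in section 3 uses week-4 data. On this view the visits are badly labelled and the science is untouched.

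Much of that stands. The before-and-after randomised design is sound on this point, and the planned analyses do not depend on the labels.

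A reader might infer more from the headings: that the primary outcome could not show any effect of beta-glucans, that all the listed variables are affected alike, or that the arms would be tested against each other at baseline with a 5 % false-positive rate as the only possible outcome. The documents do not support these readings. OGTT and stool measurements appear at both times under the primary heading, so only the lipids lack a later time there. No section plans a test of the arms at baseline. The one baseline comparison, responders against non-responders, is made within the test group.

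The reply still does not rescue the definition. If 2.3 already includes week 4, then 2.4 makes the same week-4 measurements secondary, and they hold both ranks at once. Section 2.5 applies the labels to the provision of results, so they reach beyond the text of the SAP. The protocol cannot settle the matter because it names no primary outcome.

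**Conclusion.** The outcome definition in SAP 2.3 and 2.4 is wrong as stated and contradicts itself. Primary and secondary are separated by visit, against the SAP's own sampling times for OGTT and stool, its analyses and its hypotheses. For the four lipids, the variables of the third hypothesis, the baseline label is not corrected anywhere in 2.3.

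The problem is confined to how outcomes are defined and how results are labelled and reported. Week-4 data were collected and analysed, so no data are lost, and no numerical error rate or loss of power follows from the labels. Nowhere do the documents define a primary outcome as a variable, a time point and a comparison between the breads.

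This conclusion rests on reading the section headings as assigning rank, which sections 2.4 and 2.5 bear out. It does not address which variable should rank first or how multiplicity across several primary variables should be handled; those are separate questions.

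**What to change.** - In 2.3, call the day-before sample baseline.
- Define each primary outcome as the change from baseline to four weeks, or the week-4 value adjusted for baseline, compared between test and control bread. Choose one form and state it. Give lipids an explicit four-week time in 2.3.1.
- Delete 2.4 as a repeat of the same measurements, and use secondary only for variables of lower rank. Bring the wording of 2.5 into line.
- In section 3, say which analysis belongs to the primary outcomes. For the metabolic measures this means stating a between-arm comparison, since only within-person tests are given now.
- Relabel the result tables to match.
- State that the definition is post hoc unless an earlier record supports it, because SAP section 1 says the document was prepared after the trial was completed and the protocol names no primary outcome.

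The cost is rewording the SAP, relabelling tables and, where a between-arm comparison of the metabolic measures has not been run, running it on existing values. No new data are needed.

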## 2. Oral glucose tolerance test (OGTT)

Sampling time after glucose consumption (min)	Before dietary intervention		After dietary intervention	
	Glucose level (mmol/l)	Insulin level (μU/ml)	Glucose level (mmol/l)	Insulin level (μU/ml)
0				
30				
60				
120				

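### Hypothesis 2 is about insulin resistance, but no insulin-resistance measure or main OGTT value is named, and the only stated tests for glucose and insulin are uncorrected within-arm paired tests

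*SAP*

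**What the plan says.** SAP section 1.2 states in its second hypothesis that beta-glucan consumption "has an influence on glucose metabolism and consequently improves insulin resistance". SAP section 2.3, on primary outcomes, adds: "Blood sampling was performed for insulin resistance determination".

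The data come from the OGTT described in SAP section 2.3.2. On timing, it says "OGTT was performed one day before and one day after the four-week intervention". At each visit, "Fasting blood samples were obtained for analysis of baseline glucose and insulin levels", and after the glucose load "blood samples were taken, at 30, 60 and 120 minutes". The protocol's OGTT form (part B, item 2) matches this: four rows (0, 30, 60 and 120 minutes), with glucose and insulin at each visit and no row for a derived quantity. SAP section 2.4 says only that the measurements were repeated after four weeks.

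SAP section 3 (Statistics) groups the outcomes as "anthropometric and metabolic characteristics, RT-PCR results and microbial richness and diversity measures" and gives them a Wilcoxon signed-rank test or a paired t-test, with P < 0.05 for significance and P < 0.1 for a trend. Benjamini-Hochberg correction and a model with a time, group and subject interaction are stated only for the differential abundance analysis of sequences.

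**The concern.** Three gaps meet on the same hypothesis.

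- **No endpoint.** Insulin resistance is not read directly off the OGTT form; it has to be derived from glucose and insulin. No formula is given, so an analyst could choose among several fasting or OGTT-based indices, two AUCs and eight single values.
- **No control of multiplicity.** If several of these are tested at 5% each, the chance that at least one is significant exceeds 5%, and the plan does not say which one would decide the hypothesis.
- **No randomised comparison.** A paired test within an arm asks whether values changed over four weeks. It cannot separate the effect of beta-glucans from a change shared by both arms, such as the effect of eating 200 g of study bread a day, regression to the mean after selection on risk factors, or drift between visits. The control arm exists to remove such changes, but the stated test for these variables does not use it.

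At stake is one of the trial's three hypotheses, which could be declared supported on a selected before/after difference at one time point.

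**Working it through.** The documents give no sample size, power or error rate for the glucose and insulin outcomes, so there is no planned figure to reproduce.

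**1. Count.** Four sampling times (0, 30, 60, 120 min) x 2 analytes = 8 before/after comparisons per arm, or 16 over both arms. The times and analytes come from SAP section 2.3.2 and the protocol's OGTT form. That each value is tested is an assumption; SAP section 3 does not list the variables.

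**2. Family-wise error in one arm, independent tests, no true change.**

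- Either direction, P < 0.05: 1 − 0.95^8 = 0.337.
- Favourable direction only, from the same two-sided tests: 1 − 0.975^8 = 0.183.
- Either direction at the trend level, P < 0.1: 1 − 0.90^8 = 0.570.

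**3. Correlated tests.** The correlation between OGTT values is not given, so a range is assumed. With eight normal test statistics sharing a common pairwise correlation r, the chance of at least one result beyond the threshold is:

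| Assumed r | P < 0.05, either direction | P < 0.05, favourable only | P < 0.1, either direction |
|---|---|---|---|
| 0 | 33.7% | 18.3% | 57.0% |
| 0.5 | 25.0% | 12.5% | 43.5% |
| 0.7 | 19.1% | 9.5% | 33.7% |
| 0.9 | 11.9% | 6.0% | 21.7% |

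The either-direction columns suit the first half of Hypothesis 2 (an influence on glucose metabolism). The favourable-only column suits the second half, which is directional.

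**4. Both arms tested (16 tests, arms independent).** The formula is 1 − (1 − F)², where F is the one-arm rate. At P < 0.05, either direction, this gives 1 − (1 − 0.337)² = 56% at r = 0, and 44%, 35% and 22% at r = 0.5, 0.7 and 0.9.

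**5. Within-arm testing as a substitute for a comparison.** Suppose beta-glucans do nothing, both arms share the same change over time, and each arm has chance p of reaching P < 0.05 on a given variable (arms independent). The chance that the test arm is significant and the control arm is not is p(1 − p): 0.05 x 0.95 = 4.75%, 0.2 x 0.8 = 16%, 0.5 x 0.5 = 25%. So even one pre-named variable could often show the apparent pattern of an effect. Replacing eight paired tests by one paired test would therefore not be enough.

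**6. After the change.** One named measure with one between-arm test has a false-positive chance of 5%. If all eight values were kept as formal between-arm tests, Bonferroni would require 0.05/8 = 0.00625 each.

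**The case against.** The strongest reply is that the documents show a missing definition and no more. SAP section 3 does not list its metabolic variables. Section 2.3 states an intent to determine insulin resistance, so an index may be meant to fall under that term. A collection form and a sampling schedule are not a list of tests. This stands. A reader might infer that the plan tests only separate glucose and insulin values, or commits to exactly eight tests; the documents support neither, so the error rates above are conditional.

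A reader might also infer that Hypothesis 2 is never tested. That goes too far: before/after glucose and insulin values bear on its first half. What lacks an endpoint and a named test is the insulin-resistance part.

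Two further points stand. Either-direction rates overstate the risk for a directional claim, which is why the favourable-only rates are shown. And P < 0.1 is labelled a trend in the SAP, not significance.

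It may also be tempting to argue for an AUC as generally more precise than a single time point. That is not established here. It depends on assumed SDs and correlations, says nothing about a fasting index, and does not imply more power when an effect is confined to one time point.

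The reply does not reach the absence of a between-arm test. Whatever variable is meant, the test stated for it is paired and within-subject, and the only interaction model is reserved for sequences.

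**Conclusion.** The point holds. The insulin-resistance part of Hypothesis 2 has no defined measure, no main OGTT value is chosen, no multiplicity control is stated for these outcomes, and no between-arm test of them is specified. These statements rest on the text alone.

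The size rests on assumptions: eight values each tested in one arm, normal test statistics, equal pairwise correlation, and no true change over time. On that basis the chance of at least one P < 0.05 is 34% under independence and 12% to 25% at correlations of 0.9 down to 0.5. In the favourable direction only, it is 18% and 6% to 12.5%. Each single test keeps its nominal 5%; the inflation is across the family. The missing randomised comparison matters at least as much, because it would remain even if one index were named. This should be corrected before any claim on insulin resistance is made.

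**What to change.** - **Name one measure.** State one insulin-resistance measure for Hypothesis 2 and write out its formula. Log HOMA-IR from the fasting glucose-insulin pair is one example; both inputs are on the protocol's form at both visits.
- **Compare the arms.** Analyse the week-4 value by ANCOVA, with randomised arm as the factor and the baseline value as covariate, instead of by within-arm paired tests. Report the adjusted difference with its 95% confidence interval.
- **Rank the rest.** Report glucose and insulin AUC 0-120 as supporting outcomes, compared between arms in the same way. Show single time points descriptively, or correct them for multiplicity.
- **Label the timing.** SAP section 1 says the document was prepared when the trial was completed. The chosen measure should therefore be labelled post hoc unless an earlier record of it exists; naming it now does not give it the standing of a pre-specified endpoint.

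The cost is SAP wording, a derived variable and a re-analysis of data already collected. Significance claims at single time points are given up, and an effect confined to one time point may be missed.

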#### 2.3.1. Lipid profile

All blood lipid measurements were determined with standard diagnostic methods (Roche/Hitachi Cobas c system). Total cholesterol was determined with an enzymatic method using cholesterol esterase, cholesterol oxidase and peroxidase [2]. Blood triglycerides were determined with a four-step enzymatic method involving lipoprotein lipase, glycerol kinase, L- $\alpha$ -glycerol phosphate oxidase and NAD-peroxidase [3,4]. LDL-cholesterol was determined with cholesterol oxidase and peroxidase [5]. HDL-cholesterol was determined with cholesterol esterase and cholesterol oxidase [6].

#### 2.3.2. Oral glucose tolerance test (OGTT)

OGTT was performed one day before and one day after the four-week intervention [7]. Participants fasted overnight (for at least 10 hrs). Fasting blood samples were obtained for analysis of baseline glucose and insulin levels. After the consumption of glucose solution (75 g of glucose dissolved in 250 ml of water) in five minutes time, blood samples were taken, at 30, 60 and 120 minutes. Concentrations of blood glucose were determined with a standardised spectrophotometric methodology (Roche Hitachi Cobas c system (GLUC3)). The procedure is based on hexokinase and glucose-6-phosphate dehydrogenase reaction [8]. Blood insulin was determined by immunoradiometric assay (Biosource Europe S.A., Nivelles).

